[name] is an evaluation and qualitative methods specialist with 10 years' experience in designing and managing complex, mixed method evaluations for government departments and VCS organisations, typically drawing on theories of change or leading collaborative development of logic models. [name] joined IFF in 2019, after 5 years at Kantar. She is a UK Evaluation Society, Market Research Society, Social Research Association member, and an advisor on the What Works for Children's Social Care Evaluation Advisory Group.

Education

- 2010 - 2011. MSc Social Psychology (London School of Economics)
- 2005 - 2010. BA Psychology (University of British Columbia)

Timeline

Please see the timeline outlined below:

	Responsibility	2021												2022						
		M a r	A p r i l	M a y	J u n e	J u l y	A u g	S e p	O c t	N o v	D e c	J a n	F e b	M a r	A p r	M a y	J u n e	J u l y	A u g	
Set-up meeting	All	■	■																	
Trial protocol and ethics application	PERU		■	■																
Parent recruitment	Babies 1st				■	■	■	■	■	■	■	■	■							
Parent baseline and randomisation	PERU				■	■	■	■	■	■	■	■	■							
VIG delivery	LAs				■	■	■	■	■	■	■	■	■	■	■	■	■	■		
Process evaluation fieldwork – W1	IFF					■														
Parent follow-up survey	IFF							■	■	■	■	■	■	■						
Process evaluation fieldwork – W2 (practitioners)	IFF					■	■	■	■	■										
Process evaluation fieldwork – W2 (parents)	IFF															■	■			
Analysis	PERU/IFF																		■	■
Report delivery	PERU/IFF																			■

Appendix A: Scales used in baseline and follow-up questionnaires

MORS-SF

1. My baby smiles at me
2. My baby annoys me
3. My baby likes doing things with me
4. My baby 'talks' to me
5. My baby irritates me
6. My baby likes me
7. My baby wants too much attention
8. My baby laughs
9. My baby gets moody
10. My baby dominates me
11. My baby likes to please me
12. My baby cries for no obvious reason
13. My baby is affectionate towards me
14. My baby winds me up

Warmth items: 1, 3, 4, 6, 8, 11, 13

Invasion items: 2, 5, 7, 9, 10, 12, 14

Scoring: 5 = Always; 4 = Very often; 3 = Quite often; 2 = Sometimes; 1 = Rarely; 0 = Never. No reverse scoring. Item scores are summed.

Karitane Parenting Confidence Scale

1. I am confident about feeding my baby
2. I can settle my baby
3. I am confident about helping my baby to establish a good sleep routine.
4. I know what to do when my baby cries
5. I understand what my baby is trying to tell me
6. I can soothe my baby when he/she is distressed
7. I am confident about playing my baby
8. If my baby has a common cold or slight fever, I am confident about handling this.
9. I feel sure that my partner will be there for me when I need support.
10. I am confident that my baby is doing well
11. I can make decisions about the care of the baby.
12. Being a mother/father is very stressful for me.
13. I feel I am doing a good job as a mother/father
14. Other people think I am doing a good job as mother/father
15. I feel sure that people will be there for me when I need support

Scoring: 3 = Yes, most of the time; 2 = Yes, some of the time; 1 = No, not very often; 0 = No, hardly ever. No reverse scoring. Item scores are summed.

Parental Stress Scale

1. I am happy in my role as a parent.
2. There is little or nothing I wouldn't do for my child(ren) if it was necessary.
3. Caring for my child(ren) sometimes takes more time and energy than I have to give.

4. I sometimes worry whether I am doing enough for my child(ren).
5. I feel close to my child(ren).
6. I enjoy spending time with my child(ren).
7. My child(ren) is an important source of affection for me.
8. Having child(ren) gives me a more certain and optimistic view for the future.
9. The major source of stress in my life is my child(ren).
10. Having child(ren) leaves little time and flexibility in my life.
11. Having child(ren) has been a financial burden.
12. It is difficult to balance different responsibilities because of my child(ren).
13. The behaviour of my child(ren) is often embarrassing or stressful to me.
14. If I had it to do over again, I might decide not to have child(ren).
15. I feel overwhelmed by the responsibility of being a parent.
16. Having child(ren) has meant having too few choices and too little control over my life
17. I am satisfied as a parent.
18. I find my child(ren) enjoyable.

Scoring: 5 = Strongly agree; 4 = Agree; 3 = Undecided; 2 = Disagree; 1 = Strongly disagree. Items 1, 2, 5, 6, 7, 8, 17, and 18 are reverse scored. The item scores are then summed.

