MORS-SF is a 14 item instrument which measures a parent's 'representations' of their infant's thoughts, feelings and intentions towards them. The instrument comprises two scales: 'warmth' and 'invasion', which are calculated and reported separately, and therefore form two separate co-primary outcomes in this evaluation. 'Warmth' measures the parent's model of their infant's emotional warmth towards them. It is obtained from statements such as 'my baby smiles at me' and 'my baby likes doing things with me'. 'Invasion' measures the parent's model of their infant's emotional invasion or control over them (or in other words, it measures the level by which the parent experiences their infant as disruptive and invasive), and is obtained from statements such as 'my baby annoys me' and 'my baby wants too much attention' (see Appendix A for all 14 statements). As such both scales provide a measure of the parent's relationship with the baby.

Both scales have a total possible score of 35. A score of 11 or less on the warmth scale should indicate concern. Concern on the invasion scale is indicated by a score of over 17.

Karitane Parenting Confidence Scale (KPCS)¹²

The Karitane Parenting Confidence Scale is a 15 item instrument which measures perceived parental-self efficacy (PPSE) - perceptions of confidence with regard to the parenting role. This scale will be used to provide an estimate of impact for the first co-secondary outcome consistent with the outcome 'improved parental confidence' identified as important in the development of the theory of change/logic model.

The KPCS is scored by summing across all responses with the possible range of scores being 0-45. The cut-off score is 39, such that parents scoring 39 or less may be experiencing low levels of parenting confidence.

Parental Stress Scale (PSS)¹³

The Parental Stress Scale is an 18 item instrument measuring parental stress - a parent's perceived stress relating to the parenting role. This scale will provide a measure of the 'lower parental stress' outcome identified through the logic model/theory of change process. A number of items are reverse scored, and scores are summed to give an overall score in the range 18-90. Higher scores indicate higher levels of perceived parental stress.

CSC 'step-up'

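### The Karitane confidence score adds its one stress-worded item (item 12) without reversing it, so on that item a fall in stress counts as a loss of confidence

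*Protocol*

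**What the plan says.** Appendix A lists the 15 Karitane items. Item 12 is "Being a mother/father is very stressful for me". One key follows for the whole list: "Scoring: 3 = Yes, most of the time; 2 = Yes, some of the time", and then "1 = No, not very often; 0 = No, hardly ever. No reverse scoring. Item scores are summed". No other place in the protocol gives item 12 a key of its own.

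The Outcome Measures section describes the total: "The KPCS is scored by summing across all responses with the possible range of scores being 0-45". It sets the direction through the cut-off: "The cut-off score is 39, such that parents scoring 39 or less may be experiencing low levels of parenting confidence". A higher total therefore means more confidence. On the role of the scale it says: "This scale will be used to provide an estimate of impact for the first co-secondary outcome".

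The Secondary Analysis section fits Equation [1] to this outcome, with both the follow-up score Y and the baseline covariate X taken from the scale.

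**The concern.** Item 12 is worded the opposite way to the other 14 items, yet it enters the sum with the same sign. A parent who finds parenting stressful most of the time gains three confidence points for saying so, and one who hardly ever does gains none.

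The rest of the appendix suggests an oversight. The Parental Stress Scale also mixes the two directions of wording, and there eight items are named for reversal. The MORS-SF needs no reversal because warmth and invasion are summed as separate scores. The Karitane is the only scale in the appendix that adds oppositely worded items into one total without reversal.

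The error is not neutral between the arms. The Outcomes part of the logic model expects VIG both to improve parental confidence and to lower parental stress. If it does both, item 12 as keyed works against the other items in the treatment comparison. Randomisation does not cancel this, because the outcome itself is mis-keyed.

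**Working it through.** **Inputs.** From Appendix A: 15 items, each scored 0 to 3, one key, no reversal, plain sum; item 12 is the only stress-worded item. From Outcome Measures: range 0-45, and 39 or less read as low confidence.

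**1. The plan's own range.** 15 × 0 = 0 and 15 × 3 = 45, which matches the stated range. With item 12 reversed the range is still 0-45, so a range check on the data would not reveal the problem.

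**2. Best possible answers.** With the most favourable answer to every item:
- as written: 14 × 3 + 0 = 42
- item 12 reversed: 14 × 3 + 3 = 45

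As written, 45 is reached only with the top answer on the stress item.

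**3. Error in each total.** Let x be the printed score on item 12. The plan adds x; a score running in the direction of confidence would add 3 − x. The error is x − (3 − x) = 2x − 3:

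| Item 12 answer (x) | Added as written | Added if reversed | Error |
|---|---|---|---|
| 0 | 0 | 3 | −3 |
| 1 | 1 | 2 | −1 |
| 2 | 2 | 1 | +1 |
| 3 | 3 | 0 | +3 |

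No answer gives zero error, so every complete total is off by 1 or 3 points at each wave.

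**4. Error in change.** When stress falls on item 12:
- from 3 to 0: −3 as written, +3 if reversed (6 points apart)
- from 3 to 1: −2 against +2 (4 apart)
- from 2 to 1: −1 against +1 (2 apart)

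**5. Effect on the raw treatment estimate.** Suppose VIG improves every item by the same amount d, so that item 12 falls by d.
- as written: 14d − d = 13d
- reversed: 14d + d = 15d
- understatement: 2d / 15d = 13.3%

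For illustration, an assumed d of 0.2 gives 2.6 points instead of 3.0. Without the equal-gain assumption, the raw understatement is twice the between-arm improvement on item 12. The protocol gives no item-level means or SDs, so the actual size cannot be computed.

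**6. Effect on the standardised estimate.** The plan also reports Glass's Delta, and mis-keying changes the control-group SD as well. Assume equal item variances and a common inter-item correlation r once all items point the same way. In units of one item's variance, the variance of the sum is 15 + (14 × 13 − 2 × 14)r = 15 + 154r as written and 15 + (15 × 14)r = 15 + 210r if reversed. With equal gains, the loss in standardised effect is 1 − (13/15) × √[(15 + 210r)/(15 + 154r)]:

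| Assumed r | Loss in standardised effect |
|---|---|
| 0 | 13.3% |
| 0.1 | 5.7% |
| 0.3 | 2.2% |
| 0.5 | 1.0% |

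**7. Position against the cut-off of 39.** The classification can change only when the other 14 items sum to 37, 38 or 39. Two examples:
- other items 39, item 12 = 0: total 39 (low confidence) as written, 42 (not low) if reversed
- other items 37, item 12 = 3: total 40 (not low) as written, 37 (low) if reversed

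**The case against.** Five points can be made in the plan's defence.

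- **Only a secondary outcome is affected.** This is correct. The MORS-SF co-primary outcomes, the minimum detectable effect size and the randomisation are untouched, and parental stress has its own 18-item outcome with reversal stated. This limits the consequence but does not remove the error.
- **The 13.3% is a raw-score figure.** This is also correct. With equal gains and positively correlated items the standardised loss is smaller (step 6), and the variance of the total falls, so a general claim of added noise is not established. The loss would be larger than tabulated if VIG moved item 12 more than the other items.
- **No planned analysis uses the cut-off.** This stands. The Secondary Analysis section models the summed score, so misplacement around 39 matters only for descriptive reading.
- **The total can still rise.** This is true. Points are lost on item 12 alone, at most 3 of 45, and gains on the other 14 items can outweigh them.
- **The fielded form may already carry reversed codes for item 12.** The statement about reverse scoring could then mean only that no later recoding is needed. This cannot be excluded, because neither the questionnaire as fielded nor the scale manual is at hand. But the protocol prints a single key for all items and says nothing of the kind, so an analyst following it would mis-score the item. The possibility affects how the fix should be made, not whether the text needs correcting.

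**Conclusion.** The point holds. Scored as Appendix A states, the first co-secondary outcome contains one item with the wrong sign, in both the follow-up outcome and the baseline covariate. The protocol is not merely silent here: it expressly rules out reversal.

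The size is bounded: 1 or 3 points in each total, and up to 6 points in an individual's change. The direction is toward understating a benefit on confidence if VIG lowers stress. The 13.3% raw understatement rests on equal improvement in all items; the 1.0% to 5.7% standardised range rests additionally on equal item variances and a common correlation between 0.1 and 0.5. The bias that would occur in this trial cannot be derived from the document. The conclusion assumes that the responses are coded as the printed key says.

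**What to change.** First check item 12 against the Karitane manual that the protocol already cites and against the response codes on the fielded questionnaire. Then correct Appendix A in one of two ways.

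- If the form uses the printed key, delete the statement that nothing is reversed for this scale and write: *Item 12 is reverse scored (3 becomes 0, 2 becomes 1, 1 becomes 2, 0 becomes 3); the other 14 items are scored as shown; the 15 item scores are summed.* Apply this at baseline and follow-up.
- If the form already assigns reversed codes to item 12, print that separate key in the appendix and do not recode again, since a second reversal would bring the error back.

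The cost is one line in Appendix A and, in the first case, one line in the scoring script. No new data are needed as long as item-level responses are kept. The change should be recorded before outcome data are analysed, so that the rescoring cannot look driven by results.
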